4.1.1 Dose Escalation and Determination of the Maximum Tolerated Dose (Part 1)

Dose escalation will be conducted according to a continual reassessment method (CRM) ([Section 13.5](#)). Dose levels from 3 to 300 µg/kg are possible.

However, the final number of doses will be dependent on the emergent toxicity profile and will be decided by a Dose Escalation Steering Committee (DESC) ([Section 7.3.1.2](#)). Pharmacokinetic and pharmacodynamic evaluations may also inform decision making.

The DLT observation period for dose escalation will be 1 cycle; however, the adaptive dose-escalation algorithm will incorporate cumulative DLTs occurring through Cycle 3. No intra-patient dose escalation will be allowed during the study. However, once the recommended Part 2 dose(s) is determined, patients receiving lower or higher dose levels of ADCT-301 in Part 1 may be offered continued treatment at the recommended dose.

During Part 1, the DESC may expand enrollment at doses below the current dose level being evaluated as part of the dose escalation process. Additional patients may only be added at a lower dose level provided there is at least 1 patient with documented stable disease. Not more than 10 patients in total can be treated at any dose level unless at least 3 of the 10 patients have documented partial response or better using the 2014 Lugano Classification criteria² or other appropriate measures of response ([Appendix 13.3](#)).

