### **3 Study Design**

This is a Phase 1, first in human (FIH), open-label, dose-escalation (Part 1) and expansion (Part 2) study of ADCT-301 in patients with relapsed and refractory lymphoma. The study will evaluate the safety and tolerability of ADCT-301 as monotherapy, as well as the preliminary activity, PK, PD, and formation of ADAs of ADCT-301 in patients. The patient population includes those with relapsed or refractory histologically confirmed non-Hodgkin lymphoma (NHL; including Stage  $\geq$ Ib cutaneous T-cell lymphoma [CTCL]) or Hodgkin lymphoma (HL).

In Part 1, patients will receive ADCT-301 administered as a 2-hour intravenous infusion on Day 1 of each 3-week cycle. The initial dose level for Part 1 will be 3  $\mu$ g/kg. The highest possible dose will be 300  $\mu$ g/kg. The MTD will be the highest safe dose that has at least a 60% probability that the dose-limiting toxicity (DLT) rate is less than 30%.

Dose escalation will be conducted according to a continual reassessment method (CRM). Dose levels from 3 to 300  $\mu$ g/kg are possible, but the final dose level and number of doses will be dependent on the emergent toxicity profile and will be decided by a Dose Escalation Steering Committee (DESC). PK and PD evaluations may also inform decision making. See separate DESC Plan document.

The DLT period for dose escalation is changed from 2 cycles to 1 cycle in protocol amendment 4. However, the adaptive dose-escalation algorithm will incorporate cumulative DLTs occurring through Cycle 3. No intra-patient dose escalation will be allowed during the study. However, once the recommended Part 2 dose is determined, patients receiving lower dose levels of ADCT-301 may be offered continued treatment at the recommended dose.

During Part 1, the DESC may expand enrollment at doses below the current dose level being evaluated as part of the dose escalation process. Additional patients may only be added at a lower dose level provided there is at least 1 patient with documented stable disease. Not more than 10 patients in total can be treated at any dose level unless at least 3 of the 10 patients have documented partial response or better using the 2014 Lugano Classification criteria or other appropriate measures of response.

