## 4 Statistical methods

All analyses use SAS® version 9.4 or higher. Summary tables will be organized by each dose level; if some dose levels have few patients, then dose levels could be combined into dose ranges. All available data will be used in the analyses, and important data will be included in data listings, sorted by dose level, patient, and by visit within patient. Missing data will not be imputed, except via censoring in survival analyses and as otherwise specified.

Unless otherwise noted, categorical data will be presented using counts and percentages, with the number of patients in the analysis set by treatment group as the denominator for percentages. Percentages will be rounded to one decimal place, except 100% will be displayed without any decimal places and percentages will not be displayed for zero counts. Continuous data, unless otherwise noted, will be summarized using the number of observations (n), mean, standard deviation (std), median, minimum, and maximum. Minima and maxima will be rounded to the precision of the original value, and means, medians, and 95% confidence intervals (CIs) if presented will be rounded to 1 decimal place greater than the precision of the original value. The std will be rounded to 2 decimal places greater than the precision of the original value, up to a maximum of 3 decimal places.

No hypothesis testing will be performed in this study.

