#### 4.1.3 Efficacy Analysis Set

The efficacy analysis set consists of patients who receive at least one dose of ADCT-301 with a valid baseline and at least one valid post-baseline disease assessment or patients who have documented progression of disease or death at any time after the first dose of study.

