#### **4.9.1 Overall Response Rate**

Overall response rate is defined as the proportion of patients who achieve either CR or PR as best overall response as assessed by investigators according to the Lugano Classification criteria or Global Response Score Grading Scales for CTCL patients before the start of subsequent anticancer therapy or procedure.

The order of overall response category is: CR, PR, SD, NE, PD (including disease recurrence/relapse). The overall response category will be derived based on response assessment performed on or before the start of subsequent anticancer therapy/procedure. Patients without documented subsequent anticancer therapy and/or with missing start date of anticancer therapy will be considered as not having received subsequent anticancer therapy. If a patient only has one valid disease assessment which is SD, and the assessment is within 35 days after the first dose, the overall response for this patient will be considered as NE.

The overall response rate and the corresponding 95% two-sided exact confidence interval at each dose level will be presented. Subgroup analysis may be provided if relevant.

Percent change from baseline in the sum of product of diameters (SPD) for target lesions for non-CTCL patients and mSWAT total score for CICL patients will be presented for available data in the efficacy analysis set by dose level. These data will also be displayed as a waterfall plot, with vertical bars representing the sorted values of best percent reduction for each patient.

Tumor response and lesion measurement (or mSWAT) will be listed by assessment visit.

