## **5 Interim Analyses**

No formal interim analysis is planned.

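### SAP 4.9.1 gives the ORR of a Part 1 dose level with an ordinary exact interval, though a level can pass 10 patients only if at least 3 of 10 responded, so expanded rows read too high

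*SAP*

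**What the plan says.** The gate is in both documents. SAP 3 states: "Not more than 10 patients in total can be treated at any dose level unless at least 3 of the 10 patients have documented" a partial response or better. Protocol 4.1.1 and 7.3.1.2 carry the same rule within the Part 1 escalation rules, after the sentence "During Part 1, the DESC may expand enrollment at doses below the current dose level being evaluated as part of the dose escalation process". A weaker condition applies first: "Additional patients may only be added at a lower dose level provided there is at least 1 patient with documented stable disease".

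The analysis is in SAP 4.9.1: "The overall response rate and the corresponding 95% two-sided exact confidence interval at each dose level will be presented". SAP 4 sets the layout: "Summary tables will be organized by each dose level", with the option to merge sparsely filled levels into ranges. SAP 5 adds: "No formal interim analysis is planned".

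Nowhere does either document mention the gate when it defines or reports the ORR, separate the first 10 patients at a level from later ones, or give an estimate that conditions on expansion. Neither says whether Part 1 and Part 2 patients treated at the same dose are pooled. SAP 4.9.1 names no analysis set for the ORR itself. The efficacy set of SAP 4.1.3 begins "The efficacy analysis set consists of patients who receive at least one dose of ADCT-301 with a valid baseline" and leaves out some dosed patients.

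**The concern.** The 3-of-10 rule is a look at response that decides which dose levels may grow. An ordinary exact binomial interval treats the denominator as fixed in advance. At an expanded level it is not: the first 10 patients are there together with later ones only because at least 3 of them responded. Pooling the two groups carries that selection into the reported rate.

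Expanded levels will have more patients and narrower intervals than most other rows, so a reader will tend to lean on them. The table will set them beside unexpanded levels as if the two kinds of row were comparable. ORR is the first activity measure named in the secondary objectives, and protocol 8.3 lets observed efficacy data inform the choice of Part 2 cohorts.

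**Working it through.** **Inputs from the documents.** Gate: first 10 patients, at least 3 responders (SAP 3; protocol 4.1.1, 7.3.1.2). Estimator: observed proportion with a 95% two-sided exact interval per dose level (SAP 4.9.1), computed here as Clopper-Pearson.

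**Assumptions not in the documents.** True ORR p from 10% to 40%; added patients m of 10 or 20, with 5 and 60 as extremes; the gate applied at exactly 10 evaluable patients; m not itself chosen on response. The stable-disease condition is not modelled. The documents give no operating characteristic for the gate, so there is no planned figure to reproduce.

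**Formulas.** Let X ~ Bin(10, p) be responders among the first 10 and Y ~ Bin(m, p) among later patients.

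- P(gate passed) = P(X ≥ 3).
- E[X | X ≥ 3] = 10p · P(Bin(9, p) ≥ 2) / P(X ≥ 3).
- Bias of the pooled ORR given expansion = 10/(10 + m) · (E[X | X ≥ 3]/10 − p).

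**Worked case, p = 0.20, m = 10.** P(X ≥ 3) = 1 − 0.1074 − 0.2684 − 0.3020 = 0.322. P(Bin(9, 0.2) ≥ 2) = 1 − 0.1342 − 0.3020 = 0.5638. E[X | X ≥ 3] = 2 × 0.5638/0.3222 = 3.50, so the first 10 average 35.0%. Bias = 10/20 × (0.350 − 0.200) = 0.075, and the pooled ORR averages 27.5%.

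**Given expansion** (coverage by full enumeration of X and Y):

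| True ORR | P(gate passed) | Mean ORR, first 10 | Pooled mean, m = 10 (bias, points) | Pooled mean, m = 20 (bias, points) | Coverage, m = 10 | Coverage, m = 20 |
|---|---|---|---|---|---|---|
| 10% | 0.070 | 32.1% | 21.0% (+11.0) | 17.4% (+7.4) | 88.5% | 93.5% |
| 15% | 0.180 | 33.4% | 24.2% (+9.2) | 21.1% (+6.1) | 89.6% | 95.8% |
| 20% | 0.322 | 35.0% | 27.5% (+7.5) | 25.0% (+5.0) | 97.0% | 97.4% |
| 30% | 0.617 | 39.1% | 34.5% (+4.5) | 33.0% (+3.0) | 97.2% | 97.3% |
| 40% | 0.833 | 44.7% | 42.3% (+2.3) | 41.6% (+1.6) | 97.3% | 96.9% |

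With m = 10 the lower limit lies above the truth in 11.5%, 10.4%, 3.0%, 2.8% and 2.5% of expanded levels, in the order of the rows, against a nominal maximum of 2.5%.

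Extremes: with m = 5 the bias is +14.7 points at 10% and +10.0 at 20%, with coverage 84.5% and 94.4%. With m = 60, as if about 60 Part 2 patients were pooled in, the bias is +3.1, +2.1, +1.3 and +0.7 points at 10%, 20%, 30% and 40%; coverage at 10% is 91.2%.

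**Over all levels, expanded or not** (stop at 10 if fewer than 3 respond, otherwise add m). With m = 10 the mean bias is −0.8, −2.4, −2.8 and −1.9 points at 10%, 20%, 30% and 40%; with m = 20 it is −1.0, −3.2, −3.7 and −2.6. With m = 10 the lower limit exceeds the truth in 0.8%, 1.9%, 1.0%, 1.7% and 2.1% of levels at 10%, 15%, 20%, 30% and 40%, always below 2.5%.

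**Check of the remedy.** Later patients play no part in the gate, so their ORR is unbiased given expansion. Its exact interval covers 96.3% to 99.4% (p from 10% to 40%, m from 10 to 60). The conditional estimator E[Y/m | X + Y, X ≥ 3] uses all patients and has mean exactly p given expansion. For 6/20 the pooled figure is 30.0% (exact interval 11.9% to 54.3%) and the conditional estimate 24.3%. For 9/30 they are 30.0% and 26.5%.

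**The case against.** The strongest reply is that the interval does its job over the design as run. Every dose level is to be tabulated, not only expanded ones, and over all of them the lower limit is too high in at most 2.1% of cases with 10 added. The poor conditional coverage belongs to true rates of 10% to 15%, where a level passes the gate only 7% to 18% of the time. At 20% or more, with 10 to 20 added, coverage given expansion is about 97%, and at 30% to 40% a bias of 2 to 5 points is small beside an interval that runs from 15% to 59% for 7/20. ORR is secondary, SAP 4 rules out hypothesis tests, and patient-level response listings would let a reader rebuild the split.

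All of this stands, and it lowers the severity. It does not remove the point: someone reading an expanded row sees the conditional result, and nothing in the table would say so.

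A reader might also infer that expanded levels are the ones carried into Part 2, or that the gate governs Part 2. The documents do not support either. The rule is a Part 1 cap on enrollment. The DESC determines dose levels and the MTD under the CRM and safety findings (protocol 7.3.1.2) and the recommended Part 2 dose (protocol 4.1.2), and no text makes Part 2 enrollment depend on 3 of 10 responding. Nor do they say that every treated patient enters the ORR.

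**Conclusion.** The point holds in a limited form. For a Part 1 dose level expanded past 10 under the rule, the pooled ORR overstates the true rate by roughly 2 to 11 points for true rates of 10% to 40% and 10 to 20 added patients. The bias is largest where activity is low and shrinks as patients are added. The interval is a problem mainly at true rates of 15% or less: with 10 added, coverage is 88.5% at 10% and 89.6% at 15%; with 20 added it falls below 95% only at 10%. These sizes rest on the assumed true rate, the assumed number added and a gate applied at exactly 10 evaluable patients.

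It would be tempting to conclude that the exact intervals are invalid for the trial, or that ORR is inflated overall. Neither follows: over all levels the intervals are conservative and the average bias is slightly negative. What is affected is the reading of expanded rows, and their comparison with unexpanded ones, in a descriptive secondary analysis. Severity: consider.

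**What to change.** In SAP 4.9.1, for any Part 1 dose level expanded beyond 10 under the rule:

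- keep the pooled ORR and its exact interval, with a label that the sample size depended on response;
- add the ORR with exact interval separately for the first 10 patients and for those enrolled afterwards, or give a conditional bias-adjusted estimate beside the pooled one;
- state whether Part 1 and Part 2 patients at the same dose are pooled, and name the analysis set for the ORR.

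The pooled figure need not be dropped, and no activity statement need rest on the later patients alone, since that would discard 10 patients per level. The cost is a few sentences and one extra table split, wider intervals for the subsets, and a somewhat less favourable figure at expanded levels. Trial conduct does not change.

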#### **4.9.2 Duration of Response**

Duration of response will be defined for patients with CR or PR only as the interval between the date of initial documentation of a response and the date of first documented evidence of progressive disease (based on radiographic or clinical progression at EOT/end of study [EOS]) or death. Patients who had the event after the start of subsequent anticancer therapy/procedure, or are progression-free and alive at the time of clinical cut-off, or have unknown status, will be censored at the last valid tumor assessment on or before the start of subsequent anticancer therapy/procedure or clinical cut-off time.

Duration of response will be estimated and displayed by dose levels for the efficacy analysis set using Kaplan-Meier methods (SAS® PROC LIFETEST). A Kaplan-Meier plot will be presented.

Subgroup analyses may be provided for disease subtype, disease stage, double/triple hit (yes/no), bulky disease (yes/no), age group, response to the first line and/or most recent line of prior systematic therapy (relapse: CR+PR vs. refractory: SD+PD vs. other: NE + missing), best response to ADCT-301 (CR/PR), and other relevant variables.

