| Estimated Duration of Patient Participation and Study Duration: | 
For each patient, the study will include a screening period (up to 28 days), a treatment period (until withdrawal, see below), and a follow-up period to assess disease progression and survival for up to 12 months after the last dose of study drug. The total study duration will be dependent on overall patient tolerability to the study drug and response to treatment. It is anticipated that the entire study (Parts 1 and 2) could last approximately 3 years from first patient treated to last patient completed.
 
A patient may be withdrawn from the treatment for any of the following reasons:
 
• Objective disease progression• Clinical progression• AE• Withdrawal of consent• Major protocol deviation• Required treatment delay > 21 days (except in case of potential patient benefit, which must be approved by the Sponsor)• Non-compliance, including lost to follow-up• Pregnancy• Other (e.g., development of contraindications with use of the study drug)• The Investigator determines if it is in the best interest of the patient to discontinue the patient's participation in the study.• Discontinuation of the study by the Sponsor.• Death |

| | |
|--|--|
| Efficacy Assessments: | 
Response to ADCT-301 will be assessed through the evaluation of complete response (CR), partial response (PR), progressive disease (PD), and stable disease (SD) determined by the Investigator based on the Lugano Classification Criteria (2014) and Global Response Score Grading Scales for CTCL. Disease assessments will occur every other cycle for the first 2 evaluations (6 and 12 weeks), and every third cycle (every 9 weeks) thereafter until progression or more frequently, if clinically indicated.
 
Patients who discontinue treatment for any reason other than objective disease progression will continue to be followed with scans approximately every 12 weeks from the last tumor assessment until disease progression, or initiation of a new anticancer treatment. If a patient discontinues treatment for a hematopoietic stem cell transplant, the frequency of imaging will be as per the transplant center standard of care. After documentation of disease progression or start of a new anticancer treatment, patients will be contacted by telephone approximately every 12 weeks for up to 12 months after the last dose of study drug to collect survival information.
 |

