7.1 Efficacy Assessments

Disease assessments will occur every other cycle for the first 2 evaluations (6 weeks [end of Cycle 2 \pm 1 week] and 12 weeks [end of Cycle 4 \pm 1 week]), and every third cycle (every 9 weeks [e.g., end of Cycles 7, 10, 13, etc., \pm 1 week]) thereafter until progression or more frequently, if clinically indicated. Assessments may be performed within \pm 1 week of the required timepoint and response assessment must be available prior to initiation of dosing at the subsequent cycle.

In case of dose delays, disease assessment should be maintained at the frequencies defined above and response assessment is required prior to resumption of ADCT-301 dosing (only if the interval from last scan is \geq 6/9 weeks, as applicable) to rule out disease progression.

Tumor response will be determined by the Investigator, based on the 2014 Lugano Classification Criteria ([Appendix 13.2](#)) and Global Response Score Grading Scales for CTCL ([Appendix 13.3](#)). Images will be obtained according to local site imaging requirements. Images will be required to be submitted for a central/independent review for Part 2. Submission instructions for the central/independent review will be provided in a separate manual.

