8.6.1.2 Duration of Response

Duration of response will be defined among responders (CR or PR) as the time from the earliest date of first response until the first date of either disease progression or death due to any cause. The date of disease progression will be defined as the earliest date of disease progression as assessed by the Investigator using the 2014 Lugano Classification for response for Hodgkin and Non-Hodgkin Lymphoma² ([Appendix 13.2](#)) or Global Response Score criteria for disease progression for CTCL ([Appendix 13.3](#)). For patients who have not progressed or who have died at the time of the analysis, censoring will be performed using the date of the last adequate disease assessment. In addition, patients with disease progression or death after an extended loss to follow-up will be censored at the date of the last adequate disease assessment prior to the extended loss to follow-up. Further details on censoring rules will be outlined in the SAP.

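### If it is run, the optional split of duration of response by best response (CR/PR) favours CR whenever some partial responses later become complete.

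*SAP*

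**What the plan says.** SAP section 4.9.2 defines DOR, for patients with CR or PR, as "the interval between the date of initial documentation of a response and the date of first documented evidence of progressive disease" or death. Protocol section 8.6.1.2 has the same origin: "the time from the earliest date of first response until the first date of either disease progression or death due to any cause".

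The planned display is Kaplan-Meier by dose level. The SAP then adds an optional list: "Subgroup analyses may be provided for disease subtype, disease stage" and further factors, ending with "best response to ADCT-301 (CR/PR), and other relevant variables".

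SAP section 4.9.1 says how the category is reached. "The overall response category will be derived based on response assessment performed on or before the start of subsequent anticancer therapy/procedure", and "The order of overall response category is: CR, PR, SD, NE, PD". So the best category over all scans up to new therapy counts, and CR outranks PR.

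The Protocol synopsis gives the scan times, which run up to progression: "Disease assessments will occur every other cycle for the first 2 evaluations (6 and 12 weeks), and every third cycle (every 9 weeks) thereafter".

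Neither document attaches a landmark, a time-dependent method, a clock restarted at CR, or a caution to this subgroup.

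**The concern.** The label that splits the curves can be set after the clock starts. Take a PR at week 6. It can become a CR at week 12, 21 or 30, but only if the patient has not progressed or died by then. The weeks between first response and conversion cannot contain an event, and the split credits them to the CR group. A PR patient who progresses before converting can never leave the PR group. This is guarantee-time (immortal-time) bias.

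The other factors named in the list (subtype, stage, double or triple hit, bulky disease, age group, response to earlier therapy) describe the patient before treatment. Best response to study drug is the only named factor settled during follow-up.

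At stake is how two curves side by side will be read. DOR is a named secondary measure of activity. A longer median in complete responders invites the conclusion that deeper responses last longer, and this split can show that pattern when it is not true.

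**Working it through.** The plan states no expected DOR, CR share or conversion rate, so there is no figure of its own to reproduce. The check asks what the split shows when depth and duration are unrelated.

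**From the documents:** clock from first CR or PR; best response over all later scans, CR above PR; scans at weeks 6 and 12, then every 9 weeks. For a first response at week 6, the next three scans (weeks 12, 21, 30) fall 6, 15 and 24 weeks after it.

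**Assumed:** exponential DOR with the same median for all responders; a share p in CR at first response; a probability c that a patient still in PR and event-free converts at each of those three scans; no later conversion; no censoring; event times taken as continuous.

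**Formulas.** Let λ = ln 2 / median and S(t) = exp(−λt). Conversion weights are w1 = c, w2 = c(1−c), w3 = c(1−c)².
- Proportion of initial PRs that convert: K = w1·S(6) + w2·S(15) + w3·S(24).
- CR group size: p + (1−p)K. PR group size: (1−p)(1−K).
- CR group event-free at t ≥ 24: S(t)·[p + (1−p)(w1+w2+w3)].
- PR group event-free at 6 ≤ t < 15: (1−p)·[(1−w1)S(t) − w2·S(15) − w3·S(24)]; at t ≥ 24: (1−p)(1−c)³·S(t).

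**Large case: median 26 weeks, p = 0.30, c = 0.35.**
- λ = 0.02666; S(6) = 0.852, S(15) = 0.670, S(24) = 0.527.
- K = 0.35×0.852 + 0.2275×0.670 + 0.1479×0.527 = 0.529.
- CR group: size 0.30 + 0.70×0.529 = 0.670. Median where 0.8078·S(t) = 0.335, so S(t) = 0.415 and t = 33.0 weeks.
- PR group: size 0.70×0.471 = 0.330. Median where 0.65·S(t) = 0.2356 + 0.2305 = 0.4661, so S(t) = 0.717 and t = 12.5 weeks.

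**Small case: median 26 weeks, p = 0.75, c = 0.05.**
- K = 0.0426 + 0.0318 + 0.0238 = 0.098.
- CR group: size 0.775. Median where 0.7857·S(t) = 0.387, so t = 26.5 weeks.
- PR group: size 0.225. Median where 0.2143·S(t) = 0.1127, so t = 24.1 weeks.

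Apparent medians in weeks, when the truth is the same for both groups:

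| CR at first response | Conversion per scan | CR vs PR, true median 26 | CR vs PR, true median 13 |
|---|---|---|---|
| any | 0% | 26.0 vs 26.0 | 13.0 vs 13.0 |
| 75% | 5% | 26.5 vs 24.1 | 13.3 vs 12.1 |
| 75% | 10% | 27.0 vs 22.2 | 13.6 vs 11.2 |
| 30% | 5% | 29.0 vs 24.1 | 15.0 vs 12.1 |
| 30% | 20% | 32.4 vs 18.1 | 17.8 vs 9.5 |
| 30% | 35% | 33.0 vs 12.5 | 18.7 vs 7.1 |

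**Second check, different assumptions.** A simulation of 200,000 responders per setting used the protocol's scan times, allowed conversion at every later visit, and put first response at week 6 in 70% and week 12 in 30%. It varied the true median (13, 26, 52 weeks), direct CR (0% to 75%) and conversion (0%, 15%, 30%). The CR:PR event-rate ratio, truly 1, came out between 0.20 and 0.71 in every setting with conversion, and between 0.99 and 1.01 with none.

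**Do the alternatives remove it?** Grouping by category at first response gives 26 vs 26 and 13 vs 13 weeks, because the label is fixed at time zero. In the second simulation, a landmark 9 weeks after first response gives rate ratios of 0.99 to 1.02, and so does CR as a time-dependent state.

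**The case against.** The strongest reply is about scope. The split is one item in an optional list, and the planned display is by dose level. A reader might infer that the SAP commits to this analysis; its wording only permits it. That stands.

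A reader might also infer that every complete responder carries guaranteed time. That is wrong: a patient in CR at the first responding scan carries none, and without conversion the bias is nil. When most CRs are present at first response, the CR median barely moves and the distortion lies mainly in a shortened PR group. That also stands, and it is why the size must be given as a range.

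The analysis is descriptive. The SAP plans no hypothesis test, and neither document proposes a durability claim. With an assumed 20 responders, 30% direct CR, 20% conversion per scan and a true median of 26 weeks, the difference in medians would range from about −13 to +40 weeks (5th to 95th percentile). The split could support little anyway, but noise does not cancel a bias in a known direction, and the absence of a test does not stop two medians being compared.

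Finally, response by visit and derived DOR are listed, so a careful reader could pick out the late conversions. That mitigates the problem without correcting the curves.

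**Conclusion.** The concern holds in conditional form. If the optional split is run and any first PR later becomes CR, the comparison is biased towards CR. The direction follows from the SAP's own time origin and its rule for best response. The size does not: it depends on the conversion rate and the direct-CR share, which the documents do not give. At a true median of 26 weeks, the settings tabulated run from no difference to about 33 versus 12.5 weeks.

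Two stronger readings are not supported. The documents do not show that a CR advantage seen in this trial would be wholly artefact; a real difference could exist alongside the bias. Nor is the endpoint itself at fault: overall DOR, ORR, PFS, OS and the primary safety and dose objectives do not use this grouping. It is a limited point about one secondary, descriptive display, worth correcting before the display is produced.

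**What to change.** In SAP section 4.9.2, replace best response to study drug as a DOR subgroup factor with response category (CR or PR) at the first responding assessment. A landmark analysis among patients still in response, or CR as a time-dependent state, would also serve. For complete responders, add duration of CR measured from the first CR date, without comparing it with PR.

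If DOR from first response is still shown by best response, label the groups as not comparable and say that CR membership can depend on remaining event-free.

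The cost is a wording change and one derivation. Responses are already recorded by visit, so no new data are needed. The drawback is that grouping by first response counts late CRs as PR; the separate duration-of-CR summary covers those patients.
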